7.2. Collecting, Recording and Reporting of Complications

At each contact with the subject, the Investigator will seek information on complications by specific questioning and, as appropriate, by examination. All complications definitely, probably or possibly involving the treated knee, as well as any required remedial action shall be recorded on the subject's appropriate CRF. The investigator will also be asked to assess the complication with respect to severity and relatedness to the procedure.

The minimum initial information to be captured in the subject's source document concerning the complication includes:

- Study identifier;
- Study center;
- Subject number;
- A description of the complication;
- Date of onset;
- Investigator assessment of the association between the complication and study treatment (relatedness);
- Investigator assessment of severity;
- Current status;
- Whether the complication is a major complication and reason for this classification.

The clinical course of each complication should be recorded and followed until resolution, stabilization, or until it has been determined that the surgical repair is not the cause.

Notification of Sponsor by Investigator

The Investigator shall notify the Sponsor of any Major Complication experienced by any subject entered into the study. Such Major Complications ***must*** be reported ***within 24 hours*** to the following:

Ceterix Orthopaedics [name] [name] [contact] [contact]

Within the following 48 hours, the Investigator shall provide further information, as applicable, in the form of a written narrative. As the Investigator learns it, significant new information shall be provided on an ongoing basis to the Sponsor.

Notification of IRB by Investigator

With one exception noted at the end of Section 7.2, all communication with an IRB is the responsibility of the Investigator. Investigator will comply with all IRB requirements for the reporting of complications. Copies of each report and documentation of IRB notification and receipt will be kept in the Investigator's study file.

An Investigator shall report to the Sponsor a withdrawal of approval by the Investigator's reviewing IRB as soon as a possible, but no later than 5 working days of the IRB notification of withdrawal.

Notification of Investigators and IRBs by Sponsor

The Sponsor shall notify all participating IRBs and participating Investigators of any withdrawal of approval of the study by a reviewing IRB within 5 working days after receipt of the withdrawal of approval.

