
Arthroscopy Exclusion Criteria
	
Subjects will be excluded from the study if their study meniscus lesion meets any of the following criteria at arthroscopy:
 
 • Tear pattern: primarily vertical longitudinal or radial in orientation; • Partial meniscectomy of any portion of the study meniscus extends beyond the central portion (i.e., Zone 3/“white zone”); • Intact or partially intact meniscus tear that, in the opinion of the Investigator, does not require repair; • Poor meniscal tissue quality such that it will not hold a suture; • Any portion of the meniscus repair that, in the opinion of the Investigator, is best treated using an implant other than suture; • Clinically significant (zone 1 and/or zone 2) tear in the contralateral compartment to the study meniscus; • Performance of a significant concomitant procedure intended as a therapeutic intervention on the study knee; • Arthritis in the surgical knee Modified Outerbridge Grade III or higher.

Study Visits
	
Screening (Study Visit 1): Informed consent, screening eligibility criteria, demographics, patient reported outcomes, MRI (within 6 months) and X-rays (within 6 months);
 
Procedure (Study Visit 2): Arthroscopy eligibility criteria, enrollment, meniscal-repair, images, complications; details of pathology and procedure
 
1st postop [Day 7-15] (Study Visit 3): Complications;
 
2nd postop [Day 90±7 days] (Study Visit 4): Complications, patient reported outcomes;
 
3rd postop [Day 185±14 days] (Study Visit 5): Complications, patient reported outcomes, visual examination of meniscus tear (when available);

	4th postop [Day 365±30 days] (Study Visit 6): Complications, patient reported outcomes, MRI; 5th postop [Day 730±30 days] (Study Visit 7): Complications, patient reported outcomes, X-Rays;
Rehabilitation Plan	All subjects will follow their Investigator’s preferred rehabilitation plan. At a minimum, all subjects must meet the following post-operative thresholds: 
 • Weight bearing as tolerated • Hinged knee brace locked in extension when walking (4-6 weeks), released to 90 degrees for sitting/driving • No squatting or stand up/sit down motions until after 6 weeks post-op • No cutting or pivot sports until after 6 months post-op
Sponsor	Ceterix Orthopaedics [name] [name] [contact]

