7. SAFETY MEASUREMENTS

7.1. Definitions

Complication

A complication is any untoward medical occurrence, unfavorable and unintended sign (including clinically significant abnormal laboratory finding), symptom, or condition experienced by the subject and temporally associated with the procedure whether or not considered related to the procedure.

Major Complication

Any complication attributable to the meniscal repair procedure that, in the view of either the Investigator or Sponsor, results in any of the following outcomes:

- Death;
- Life-threatening illness or injury;
- Inpatient hospitalization or prolongation of existing hospitalization;
- Persistent or significant incapacity or substantial disruption of the ability to conduct normal life functions;

- Important medical events that, based upon appropriate medical judgment, require medical or surgical intervention to prevent one of the above outcomes.

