5.2 Safety Endpoint(s)

Safety follow-up includes reporting of a:

Complication

A complication is any untoward medical occurrence, unfavorable and unintended sign (including clinically significant abnormal laboratory finding), symptom, or condition experienced by the subject and temporally associated with the procedure whether or not considered related to the procedure.

Major Complication

Any complication attributable to the meniscal repair procedure that, in the view of either the Investigator or Sponsor, results in any of the following outcomes:

- Death;
- Life-threatening illness or injury;
- Inpatient hospitalization or prolongation of existing hospitalization;

CONFIDENTIAL AND PROPRIETARY

This document contains information that is confidential and proprietary to Smith & Nephew PLC and Smith & Nephew, Inc. and is intended for use only by Smith & Nephew and its manufacturer. It shall not be reproduced or copied in whole or in part, nor shall the contents be disclosed by any means without prior written permission from Smith & Nephew, nor shall anyone make any use of it that is contrary to the expressed or implied wishes of Smith & Nephew

Statistical Analysis Plan	Smith+Nephew
A Prospective, Non-randomized, Multi-Center Investigation of All-suture-based Repair of Horizontal Meniscal Tears (STITCH Study)	Number: CTX-CP001
	Version: 1, 4-Sept-2019
	Page: 7 of 15

- Persistent or significant incapacity or substantial disruption of the ability to conduct normal life functions;
- Important medical events that, based upon appropriate medical judgment, require medical or surgical intervention to prevent one of the above outcomes.

6. Statistical Considerations

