- the incidence according to subjects with at least one new complication,
- the incidence according to subjects with at least one new major complication,
- the incidence according to subjects whose complication was related to fall or injury,
- the incidence according to subjects who had at least one complication possibly, probably, or definitely related to surgical procedure,
- the incidence according to subjects who had at least one complication possibly, probably, or definitely related to meniscal repair, and
- the incidence according to subjects who had at least one complication possibly, probably, or definitely related to device(s) used.

A summary table will be presented that summarizes the complications by code according to subjects who had at least one new complication of a particular code.

In addition, for each complication, the following will be summarized: the relationship to the surgical procedure, the relationship to meniscal repair, the relationship to device(s) used, outcome and duration of the resolved complications and the duration of the complications at study discontinuation.

A listing of all new complications per subject will also be presented, along with duration, major complication status (yes/no), resolution status (resolved or ongoing), and relatedness to surgical procedure, meniscal repair, and device(s) used.

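### The SAP reports the incidence of all complications, but the protocol requires CRF entry only for those that may involve the treated knee, so the figure can be too low against its own definition

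*Protocol*

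**What the plan says.** Three parts of the plan bear on this.

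- **Definition.** Protocol 7.1 opens: "A complication is any untoward medical occurrence, unfavorable and unintended sign (including clinically significant abnormal laboratory finding), symptom, or condition experienced by the subject". The event must be "temporally associated with the procedure whether or not considered related to the procedure". No body site is named. SAP 5.2 carries the same definition over as the safety endpoint, beginning "A complication is any untoward medical occurrence, unfavorable and unintended sign".
- **Recording.** Protocol 7.2 requires entry on the CRF, along with any remedial action, for this class: "All complications definitely, probably or possibly involving the treated knee". Protocol 8.4 describes the CRF as the main instrument for collecting study data.
- **Reporting.** SAP 7.10 (Analysis of Safety Endpoints) plans counts and percentages in the Safety Population. The first is "the incidence according to subjects with at least one new complication". Neither that line nor the tables and listing after it are restricted to the knee.

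Protocol 7.2 also provides a separate route. The investigator notifies the sponsor of any Major Complication within 24 hours, wherever in the body it occurs. Under Protocol 7.1 a Major Complication must be attributable to the meniscal repair procedure, in the view of the investigator or the sponsor, and must lead to one of the listed serious outcomes.

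**The concern.** The endpoint is defined and reported for one class of events, while mandatory data capture covers a narrower class. An anaesthetic reaction, a systemic illness or a problem in another limb, if temporally associated with the surgery, is a complication under Protocol 7.1. Nothing requires it on a CRF unless it may involve the treated knee.

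SAP 7.10 tabulates relation to the surgical procedure separately from relation to the meniscal repair and to the devices. Harms of the operation as a whole are therefore meant to be visible, and some of these are the events most likely to lie outside the knee. In a single-arm study of about 30 subjects, a reader would take a low count as evidence about all complications, when the recording rule supports a statement about knee complications only.

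**Working it through.** The plan states no complication rate and no precision target for safety, so there is no figure to reproduce. The check is a comparison of texts, followed by an illustration on assumed rates.

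**Step 1: follow a non-knee event through the plan.**

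| Stage | Source | Non-knee, not a Major Complication | Non-knee Major Complication |
|---|---|---|---|
| Meets the definition | Protocol 7.1, SAP 5.2 | Yes, if temporally associated | Yes, if temporally associated |
| CRF entry required | Protocol 7.2 | No | No |
| Sponsor notice required | Protocol 7.2 | No | Yes, within 24 hours |
| Counted in SAP 7.10 | SAP 7.10 | Only if entered anyway | Only if entered anyway or added from the notice; no rule is given |

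The first group includes events with a serious outcome that are judged not attributable to the repair procedure.

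**Step 2: direction of the error.** Let K be the proportion of subjects with at least one complication that may involve the treated knee. Let q be the proportion whose complications are all non-knee. Incidence under the definition is K + q. If sites record no more than 7.2 requires, reported incidence is K. The shortfall is q, which cannot be negative. A non-knee event in a subject who already has a recorded knee complication leaves this subject-level figure unchanged.

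**Step 3: illustration.** q is assumed. n is 30 if the Safety Population is everyone treated (SAP 7.2), or 30 − 3 = 27 if the three exclusions in SAP 6.1, described there as applying to all analyses, extend to safety. With independent subjects, the expected number missed is nq and the chance of missing at least one is 1 − (1 − q)^n.

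| Assumed q | Expected missed, n = 30 | Chance of at least one, n = 30 | Expected missed, n = 27 | Chance of at least one, n = 27 |
|---|---|---|---|---|
| 1% | 0.3 | 1 − 0.99^30 = 26.0% | 0.27 | 23.8% |
| 2% | 0.6 | 1 − 0.98^30 = 45.5% | 0.54 | 42.0% |
| 5% | 1.5 | 1 − 0.95^30 = 78.5% | 1.35 | 75.0% |
| 10% | 3.0 | 1 − 0.90^30 = 95.8% | 2.7 | 94.2% |

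**Step 4: effect on a reported percentage, with assumed counts.** Suppose 3 of 30 subjects have a recorded knee complication and 3 others have non-knee complications only. The table shows 3/30 = 10.0% (exact 95% interval 2.1% to 26.5%). Under the definition it should show 6/30 = 20.0% (7.7% to 38.6%). With one such subject instead of three, the correct figure is 4/30 = 13.3% (3.8% to 30.7%). The intervals only give scale, since SAP 7.10 itself specifies counts and percentages.

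**The case against.** The best defence is that Protocol 7.2 sets a minimum and does not forbid recording anything else. The same section says that at each contact "the Investigator will seek information on complications by specific questioning and, as appropriate, by examination", without a knee limit. It lists the details to be kept in the source document for a complication, again without that limit, and asks for each complication to be followed to an outcome. The forms themselves (CRF-006 Safety Follow-Up and CRF-007 Complication) are not in the text, and the derived flags in SAP 7.4 suggest fields for falls, surgery, repair, devices and death. Sites may have recorded non-knee events voluntarily.

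This stands as a limit on the wording. It cannot be said that non-knee events never reach the database, or that the incidence will be understated. It does not remove the mismatch, because the general recording language does not name the CRF and SAP 7.10 describes no reconciliation with source documents. The 24-hour notice narrows the gap for serious, attributable harms but does not cover the rest.

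A reader might infer three stronger points that the documents do not support:

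- **That relatedness is judged before an event is recorded.** The filter in 7.2 is anatomical. Knee events unrelated to the procedure still have to be recorded, and relatedness is assessed separately.
- **That the day of surgery has no safety form.** The synopsis has "Procedure (Study Visit 2): Arthroscopy eligibility criteria, enrollment, meniscal-repair, images, complications", while the activity schedule marks Safety Follow-Up only from Visit 3. But CRF-007 is a separate form, and 7.2 applies at each contact. A missing schedule mark does not show that complications at Visit 2 could not be recorded.
- **That the report would show zero non-knee events in 30 subjects.** SAP 7.10 plans no non-knee row.

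**Conclusion.** The mismatch between definition, recording rule and reported incidence is real, and no other section resolves it. If the recording rule is followed as written, the reported proportion of subjects with at least one complication is equal to or below the proportion under the plan's own definition. The shortfall is unknown. It equals the share of subjects whose complications are all non-knee and unrecorded.

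The probabilities above rest on assumed shares of 1% to 10%, on independence between subjects, and on sites recording no more than is required. They show that missing at least one subject is plausible at this sample size, not that it happened. Protocol 7.1 gives no time window for temporal association, so late events remote from the knee may not meet the definition at all, which would make the true share smaller. The point should be fixed because it affects how the safety tables can be read; it does not touch the reoperation or patient-reported endpoints.

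**What to change.** **If collection can still be changed:** amend Protocol 7.2 so that every complication meeting the 7.1 definition is recorded on CRF-007, and add a field for involvement of the treated knee. This costs one sentence, one field and slightly more data entry. The reported complication rate may rise a little.

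**If not:** SAP 6.1 says the sample was already accrued, so this is the more likely course.

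- Label the SAP 7.10 tables and listing as complications involving the treated knee, plus any others recorded.
- Compare the sponsor's Major Complication notices with the CRFs, and add any that are missing. Where feasible, check source documents in the same way.
- State with the tables that CRF recording of non-knee complications was not required.
- State whether the safety denominator is 30 or 27, since SAP 6.1 and SAP 7.2 can be read differently.

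This costs new table titles, one reconciliation and a short limitation statement. The safety claim becomes narrower, but it then matches what was required to be collected.

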1. ABBREVIATIONS, ACRONYMS AND DEFINITIONS

All Suture-Based Technique: A repair technique (all-inside, inside-out, outside-in or combination thereof) utilizing only suture without implanting any other material intended to anchor and/or replace suture material.

BMI: Body Mass Index

Complex Tear: Multiple discreet tears, tears with multiple planes, or meniscal tissue incapable of holding suture.

Consented Patient: A patient who, after the screening process, grants consent to participate in the trial.

CFR: Code of Federal Regulations

CRF: Case Report Form; includes all study forms.

Enrolled Subject: A patient who has been consented, meets all criteria for inclusion immediately prior to treatment and receives all suture-based repair of meniscal tear.

HT: Horizontal tear (of the meniscus); the majority of the tear is oriented primarily (but not exclusively) parallel to the plane of knee joint dividing the structure into superior and inferior flaps. For the purpose of this protocol, HT includes obliquely-oriented tears. These tears may open at the central apex or along the inferior surface of the meniscus. Some horizontal tears may have a radial component (bird beak) in the central White Zone.

HIPAA: Health Insurance Portability and Accountability Act

IKDC: International Knee Documentation Committee

IRB: Institutional Review Board

ISAKOS: International Society of Arthroscopy, Knee Surgery and Orthopaedic Sports Medicine

KOOS: Knee injury and Osteoarthritis Outcome Score

PCL: Posterior Cruciate Ligament

Protocol Deviation: A protocol deviation is any change, divergence, or departure from the study design or procedures of a research protocol that is under the Investigator's control and that has not been approved by the IRB.

Protocol Violation: A protocol violation is a deviation from the IRB-approved protocol that may affect the subject's rights, safety, or well-being and/or the completeness, accuracy and reliability of the study data.

Red Zone: The well-vascularized peripheral-most ~30% of the meniscus.

Red-White Zone: The transition between the outermost and innermost portions of the meniscus where vascularity diminishes from peripheral to central.

Subject: A consented patient who has been enrolled in the study.

White Zone: The inner (avascular) one-third of the meniscus.

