5.2. Criteria for Recruitment

a. Diagnosis and Main Criteria for Enrollment

Subjects will be recruited for the study through the clinical practices of the Investigators. The study population includes otherwise healthy subjects with a symptomatic meniscus tear, who are able and willing to participate and who qualify for study inclusion based on specific eligibility criteria.

The presence of some inclusion or exclusion criteria cannot be detected by preoperative clinical or radiologic evaluations and it is only after the surgeon has inserted the arthroscope to inspect the knee joint visually that the presence of such injuries or disorders can be detected. Consented subjects will only be enrolled at the time of arthroscopy provided a qualifying meniscal tear is confirmed, no other exclusionary findings are encountered and the meniscal tear is surgically treated.

b. Inclusion Criteria

Screening Inclusion Criteria:

Subjects of either gender *may be* eligible for inclusion in the study only if they meet *all* of the following criteria:

- Able and willing to give informed consent by voluntarily providing written informed consent in accordance with governing Institutional Review Board
- 18 to 60 years of age, inclusive at the time of screening;
- History indicative of meniscal pathology (e.g., pain, mechanical symptoms described as locking, clicking or giving way);
- Physical exam consistent with meniscus tear (e.g., locked joint, joint line tenderness and/or pain on meniscal compression);

- If prior ligament reconstruction, the study knee is clinically stable;
- Preoperative MRI evidence within 6 months consistent with a horizontal/oblique meniscus tear in the symptomatic compartment
- Healthy and not pregnant

Arthroscopy Inclusion Criteria:

Consented subjects **may be** included in the study only if, upon arthroscopic inspection, their meniscal study lesion meets **all** of the following criteria established by the International Society of Arthroscopy, Knee Surgery and Orthopaedic Sports Medicine (ISAKOS) (see Appendix 1):

- Zone location: circumferential location of tear includes locations within 10mm of the peripheral rim of the meniscus;
- Radial location: any location from anterior to posterior;
- Tear pattern: primarily horizontal or oblique in orientation (not to exceed 45 degrees from horizontal);
- Compartment: either lateral or medial, but not both;

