- Opposite compartment meniscal tear (if present) limited to the central portion (i.e., Zone 3/“white zone”);
- Tear amenable to repair with all suture-based techniques.

c. Exclusion Criteria

Screening Exclusion Criteria:

Subjects **will be** excluded from the study for **any** of the following reasons:

- Arthritis in the study knee (Kellgren-Lawrence Grade 3 or higher [See Appendix 4]);
- Body Mass Index (BMI) ≥ 35 kg/m²;
- Previous meniscal repair or meniscectomy of the study meniscus;
- Unstable knee;
- Malalignment (> 5 degrees) of the study knee, based on X-ray within 6 months requiring osteotomy and/or requiring correction;
- History of constitutional/systemic inflammatory/arthritis problem or pain condition, history of knee infection, vascular condition of legs, benign neoplasms of knee, hepatitis, HIV, drug/alcohol abuse, tobacco abuse, cancer;
- Expected to undergo any other primary treatment of the knee;
- Any concomitant painful or disabling disease, condition or post-procedure status of either lower extremity that would interfere with evaluation or rehabilitation of the study knee.
- Pregnant or planning to become pregnant in the next 2 years.

Arthroscopy Exclusion Criteria:

Subjects **will be** excluded from the study if their study meniscus lesion meets **any** of the following criteria at arthroscopy:

- Tear pattern: primarily vertical longitudinal or radial in orientation;
- Partial meniscectomy of any portion of the study meniscus extends beyond the central portion (i.e., Zone 3/“white zone”);
- Intact or partially intact meniscus tear that, in the opinion of the Investigator, does not require repair;
- Poor meniscal tissue quality such that it will not hold a suture;
- Any portion of the meniscus repair that, in the opinion of the Investigator, is best treated using an implant other than suture;
- Clinically significant (zone 1 and/or zone 2) tear in the contralateral compartment to the study meniscus;
- Performance of a significant concomitant procedure intended as a therapeutic intervention on the study knee;
- Arthritis in the surgical knee Modified Outerbridge Grade III or higher [See Appendix 2 and 3]).

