Investigator-specific standard-of-care arthroscopy will be performed. Intraoperative eligibility criteria will be evaluated. If **all** of the arthroscopy inclusion criteria are met and **none** of the arthroscopy exclusion criteria are met, the subject will be eligible for study enrollment. The subject is officially enrolled in the trial when the meniscal repair is completed.

Meniscal Repair Procedure

The Investigator will follow standard all-inside and/or inside-out, and/or outside-in, and/or NovoStitch arthroscopic procedures:

- Recommended spacing of sutures is 5mm;
- Video, still photographs and diagrams of the arthroscopy procedure will be captured for documentation of meniscal tear, tear preparation and tear treatment parameters. Images and diagrams will be provided to the sponsor. All patient identifying information should be removed prior to transferring images to the sponsor.

The ISAKOS Questionnaire documenting details of the meniscus tear and required excision (if any) will be completed (CRF-004, Details of Pathology). Details of the procedure will be documented (CRF-005, Details of Procedure) will be completed. It contains questions regarding the following:

- Number and configuration of sutures used;
- Repair technique and instruments;
- Meniscal repair time recorded from intraarticular introduction of suture to transection of final suture knot;
- Other intraoperative findings.

Rehabilitation Procedure

All subjects will follow their Investigator's preferred rehabilitation plan based on the particular tear and repair characteristics. At a minimum, all subjects must meet the following post-operative thresholds:

- Weight bearing as tolerated
- Hinged knee brace locked in extension when walking (4-6 weeks), released to 90 degrees for sitting/driving
- No squatting or stand up/sit down motions until after 6 weeks post-op
- No cutting or pivot sports until after 6 months post-op

c. First Follow-up [7-15 days] (Study Visit 3)

Subjects will be evaluated and a safety follow-up will be completed.

d. Second Follow-up [90 Day \pm 7 days] (Study Visit 4)

All subjects will be evaluated and a safety follow-up form will be completed. In addition all subjects will complete the following:

- KOOS
- IKCD Knee Evaluation
- Lysholm Knee Questionnaire
- Tegner Activity Scale

e. Third Follow-up [185 Day \pm 14 days] (Study Visit 4)

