7.2 Analysis Populations

Safety Population (SAF): all subjects who receive study treatment. This population include all enrolled subjects who receive the protocol-defined treatment of suture-based meniscal repair. This will be used for summaries of disposition of the subjects, protocol deviations/violations, and safety.

Analysis Population (AS): all SAF subjects with no significant protocol deviations, meet the inclusion/exclusion criteria, and did not withdraw early (except for closure at any time). This population will be used for supportive evidence of the primary variable.

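### Safety tables count only completed repairs, so harm in an abandoned repair attempt is left out of them, and the duty to report it to the sponsor is unclear

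*Protocol*

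**What the plan says.** Protocol 1 gives the definition "Subject: A consented patient who has been enrolled in the study". The same section describes an enrolled subject as a consented patient who "meets all criteria for inclusion immediately prior to treatment and receives all suture-based repair of meniscal tear". Protocol 6.2b fixes the moment: "The subject is officially enrolled in the trial when the meniscal repair is completed". Protocol 5.2a agrees that enrolment at arthroscopy needs a confirmed qualifying tear and that "no other exclusionary findings are encountered and the meniscal tear is surgically treated".

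On safety, Protocol 7.1 defines a complication as an untoward event "experienced by the subject and temporally associated with the procedure whether or not considered related to the procedure". Protocol 7.2 has complications recorded on the subject's CRF and requires the investigator to tell the sponsor within 24 hours of "any Major Complication experienced by any subject entered into the study".

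SAP 7.2 first describes the Safety Population as everyone who receives study treatment, then specifies: "This population include all enrolled subjects who receive the protocol-defined treatment of suture-based meniscal repair". SAP 7.10 runs all safety analyses on that population.

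Other sections point to an earlier start. The Protocol 2 synopsis lists enrolment ahead of the repair at Visit 2 and lists complications at that same visit. Protocol 5.2a speaks of consented subjects who are yet to be enrolled, and Protocol 6.2a calls patients provisionally enrolled before arthroscopy.

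**The concern.** A repair can be started and not finished. One arthroscopy exclusion in Protocol 5.2 is "Poor meniscal tissue quality such that it will not hold a suture"; another is a repair judged better served by an implant other than suture. Either may become apparent only once suturing is tried. Protocol 3.1 itself says that suture techniques have been hard to use successfully on horizontal tears, and that the study is meant to document whether they can be repaired.

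If such a patient is harmed during the attempt, entry to the safety tables depends on how the procedure under study turned out. That is selection on outcome. It works against the events most plausibly caused by the technique, namely those that made the surgeon stop. In a study of 30 subjects a single omitted event changes the reported picture. Separately, if sites differ on whether such a patient is a subject, some will complete the complication form and notify the sponsor and others will not.

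**Working it through.** The documents state no figure on this point, so there is none to reproduce. The check is a trace of the defined terms, followed by an illustration of size.

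**Counting.**
1. A subject is an enrolled patient (Protocol 1).
2. An enrolled patient has received the all-suture repair (Protocol 1), and enrolment takes effect when the repair is complete (Protocol 6.2b).
3. The Safety Population is enrolled subjects who receive the protocol-defined repair (SAP 7.2).
4. Every safety summary uses that population (SAP 7.10).

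A patient whose repair is started and abandoned fails steps 2 and 3. That patient adds 0 to the numerator and 0 to the denominator of every safety table. If enrolment were instead taken to come before the repair, as the synopsis lists it, step 3 would still require receipt of the repair. Nothing says that partial suturing counts as receipt.

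**Reporting.** Set side by side:
- Protocol 1 and 6.2b: not a subject until the repair is completed.
- Protocol 5.2a and 6.2a: patients are called subjects at consent and screening, and provisionally enrolled before surgery.
- Protocol 2 synopsis: enrolment, then repair, with complications collected at the same visit.
- Protocol 7.2: notice covers subjects who have entered the study, a term that is not defined. The minimum record needs a subject number, and the example in Protocol 8.2 numbers by order of enrolment.
- Protocol 14: Safety Follow-Up starts at Visit 3, with no entry at Visit 2.

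The first, fourth and fifth items lean towards no duty; the second and third lean towards a duty. The text does not settle it.

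**Size, illustration only.** The 30 completed repairs are the planned enrolment (Protocol 5.1; SAP 6.1). The numbers of abandoned attempts and of harms are assumed. The interval is Clopper-Pearson, which SAP 7.9 uses for its proportions; SAP 7.10 itself plans only counts and percentages. For x events in n patients, the lower limit is the 0.025 quantile of Beta(x, n − x + 1) and the upper limit is the 0.975 quantile of Beta(x + 1, n − x). When x = 0 the lower limit is 0 and the upper limit is 1 − 0.025^(1/n).
- No event among 30 completed repairs: 0/30 = 0%, upper limit 1 − 0.025^(1/30) = 11.6%.
- One abandoned attempt, with harm: 1/(30 + 1) = 3.2% (0.1 to 16.7%).
- Five abandoned attempts, one with harm: 1/(30 + 5) = 2.9% (0.1 to 14.9%).
- Five abandoned attempts, none with harm: 0/35 = 0%, upper limit 1 − 0.025^(1/35) = 10.0%.

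Counting attempts can therefore move the result either way.

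**The case against.** The strongest case on the other side is that the protocol does not hold to its own definition of subject. It uses the word for patients who have only been screened or consented, its synopsis puts enrolment before the repair with complications collected at that visit, and the 24-hour duty speaks of entry, not enrolment. Investigators must also meet their IRB's complication-reporting rules (Protocol 7.2) and oversee safety at their site (Protocol 7.3). The CRFs are listed only by title, so the complication form may be wider than the text suggests. All of this stands. A reader might infer that harm in an abandoned repair would go unreported; the documents do not support that. They leave the duty to the sponsor ambiguous, and an IRB report may still be required.

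A reader might also infer that this gap deprives other sites of timely warning. It does not: even for enrolled subjects, Protocol 7.2 requires the sponsor to tell other sites only about a withdrawal of IRB approval.

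On counting, it can be said that the opening sentence of SAP 7.2 is broad enough to take in anyone treated. The next sentence narrows it to enrolled subjects who receive the repair, so this part of the objection fails on the text as written.

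**Conclusion.** The counting gap holds: under Protocol 1 and 6.2b with SAP 7.2 and 7.10, a consented patient harmed in an abandoned repair is absent from every safety table. This rests on reading receipt of the protocol-defined repair as a completed repair, which is what Protocol 6.2b indicates. The reporting gap holds only as an ambiguity that different sites could resolve differently.

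The size is unknown. The shift from 0% (upper limit 11.6%) to about 3% (upper limit 14.9 to 16.7%) assumes one harmed patient among one to five abandoned attempts. It shows what one event can do at this sample size. A reader might take it as evidence that the trial's complication rates are understated; nothing in the documents shows that any such case occurred. The point deserves correction because the exclusion depends on the outcome of the procedure and is cheap to remove.

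**What to change.** **Protocol.** Reconcile the statements on enrolment in Protocol 1, the Protocol 2 synopsis, 5.2a, 6.2a and 6.2b. State in 7.1 and 7.2 that safety recording and sponsor notification cover every consented patient from the start of the study arthroscopy, whether or not the repair is completed. The latest acceptable start is the first intra-articular introduction of suture, which 6.2b already uses to time the repair, but that would miss harm during inspection or tear preparation.

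**SAP.** In 7.2, define the Safety Population as all consented patients in whom suture repair was attempted. Show completed and abandoned attempts separately in the disposition tables (7.6) and safety tables (7.10). Leave the efficacy population unchanged.

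**Conduct.** SAP 6.1 says the planned sample was accrued, so new wording cannot by itself recover events that were never collected. Ask sites to identify any consented patient whose repair was started and abandoned, with any associated harm. If that cannot be done, say in the report that such harms were not systematically collected.

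**Cost.** Revised wording, a small source check at up to 10 sites, a complication form for any harm found, and possibly slightly less favourable complication rates.
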